## 3.2 Phase 1a Escalation (Completed)

### 3.2.1 Dose Advancement and MTD Determination

A minimum of 3 subjects will be treated in each dose cohort in a conventional 3 + 3 design ([Table 3-1](#)) starting at Cohort 1. Given the potential risk for cytokine release syndrome, the first subject in each dosing cohort will be treated and observed for 72 hours before the next subject can receive their first infusion of TTI-621. Cohort 0 represents a contingency de-escalation dose level in the event that tolerance issues are encountered in Cohort 1. Treatment for an individual subject is described in [Section 6.3](#).

**Table 3-1: TTI-621 Dose Levels by Cohort**

Cohort	N	Dose (once weekly)
0	3 (+ 3)	0.01 mg/kg
1	3 (+ 3)	0.05 mg/kg
2	3 (+ 3)	0.1 mg/kg
3	3 (+ 3)	0.3 mg/kg
4	3 (+ 3)	1 mg/kg
5	3 (+ 3)	3 mg/kg
6	3 (+ 3)	10 mg/kg

Subjects will receive TTI-621 at the assigned dose once weekly for a planned 3 weeks of treatment/observation for DLT assessment. In the absence of DLT (as defined in [Section 3.2.2](#)) in 3 evaluable subjects within a cohort, dose advancement will proceed through the successive cohorts. All subjects in each dose cohort must have completed the DLT observation period before the next dose cohort commences treatment.

Subjects will be considered evaluable for DLT if they received all 3 weekly doses within the specified treatment/observation period or if they experienced an AE meeting the criteria for DLT during that time. Those who drop out of the study during the first 3 weeks for reasons other than toxicity or who experience a delay in dosing of more than 3 days for reasons other than DLT are considered unevaluable for DLT and will be replaced with a new subject enrollment. For subjects who experienced a treatment delay, the DLT observation period will extend 7 days beyond the third dose of TTI-621.

If DLT as defined below is encountered in 1 subject within a particular dose cohort, additional subjects will be treated in that cohort as outlined in [Table 3-2](#). Based on the incidence of DLT, the MTD will be determined. Depending upon the tolerance at a particular dose level, intermediate dose levels may be studied to more closely characterize DLT and more accurately identify the MTD as recommended by the Safety Review Committee (SRC).

**Table 3-2: Dose Escalation Rules**

If DLT was observed in:	Then:
0 of 3 subjects	Proceed with enrollment in next cohort
1 of 3 subjects	Enroll 3 additional subjects in current cohort
1 of 6 subjects	Proceed with enrollment in next cohort
$\geq 2$ of 6 subjects	Do not escalate; enroll 3 additional subjects in previous cohort or new intermediate dose level
$\geq 2$ of 3 subjects	Do not escalate; enroll 3 additional subjects in previous cohort or new intermediate dose level

Individual subjects may continue receiving additional TTI-621 treatment until disease progression, unacceptable toxicity, or other reason for treatment discontinuation. As of Protocol Amendment 6, intrasubject dose escalation may be employed for active subjects in the dose-escalation phase of the study (see [Section 1.8.3](#)).

### **3.2.2 Definition of Maximum Tolerated Dose**

The MTD is defined as the dose level immediately below that in which 2 or more of either 3 or 6 subjects experienced DLT during the first 3 weeks of treatment. At least 6 subjects must be treated at the putative MTD, with no more than 1 incident of DLT. AEs that manifest after the 3-week DLT observation period or cumulative toxicities will be considered in the final definition of MTD.

The final determination of the optimal dose for further use in the expansion phase may or may not be synonymous with the MTD but will consider both acute and cumulative toxicities; the incidence of required dose delays, reductions, and discontinuations; and the overall facility of administration in clinical practice.

## **3.3 Phase 1b Expansion**

### **3.3.1 Phase 1b - Part 2 and Part 3**

In Part 2 of the expansion phase of the study, the safety and preliminary anti-tumor activity of TTI-621 monotherapy at the optimal dose identified in the escalation phase will be explored in 12–15 subjects per cohort type, as outlined in [Table 3-3](#) below. These cohorts include: indolent B-cell lymphomas (IBCL; see [Appendix A](#)), aggressive B-cell lymphomas (ABCL; see [Appendix A](#)), T-cell lymphoma (TCL), HL,

CLL, ALL, multiple myeloma (MM), AML, MDS, myeloproliferative neoplasms (MPN), and SCLC. A cohort of subjects with CD20-positive malignancies will also be enrolled and treated with TTI-621 in combination with rituximab. Similarly, a cohort of subjects with cHL will be treated with TTI-621 plus nivolumab. If preliminary evidence of clinical benefit is observed in association with acceptable tolerability, one or more hematologic disease-specific cohorts may be expanded to a maximum of 40 subjects (see [Section 8.3](#) for details). In the rare instance that a subject has more than one malignancy, the subject will be assigned to a single cohort based upon the Investigator's assessment of the subject's greatest clinical need.

In Part 3 of the expansion phase of the study, the safety and preliminary anti-tumor activity of TTI-621 monotherapy will be further explored in two cohorts of CTCL and PTCL subjects ((consisting of T- and NK-cell neoplasms per WHO definition (Swerdlow et al., 2016)), starting with the optimal dose identified in the escalation phase. Dose intensification to a maximum of 0.5 mg/kg/week will be required for all newly enrolled subjects per [Section 6.5.4](#), following a ramp-up schedule (2 weeks of study treatment at 0.2 mg/kg followed by dose intensification between week 3 and week 8 at increments of 0.1 mg/kg/week as tolerated up to maximum dose of 0.5 mg/kg/week). The overall response in each of the 2 cohorts (CTCL and PTCL) will be evaluated separately using the Simon 2-stage design.

As of Protocol Amendment 9, enrollment will be limited to the following disease types: CD20+ NHL (in combination with rituximab), cHL (in combination with nivolumab), CTCL and PTCL.

Treatment may continue until evidence of unequivocal disease progression is seen (see [Section 7.14.1](#)), unacceptable toxicity, or other reason for treatment discontinuation. For patients who have been given weekly infusion of TTI-621 for more than a year and are receiving clinical benefit (objective response or clinically meaningful long-term stable disease), investigators may exercise their discretion to reduce the dosing frequency from weekly to bi-weekly following the discussion and approval from the sponsor or designees.

An overview of monotherapy and combination treatments administered in the expansion phase is provided in [Table 3-3](#). Starting doses of TTI-621 are shown; intrasubject dose-intensification is required as outlined in [Section 6.5.4](#).

**Table 3-3: Disease Cohorts and Schedule of Treatments Administered  
in the Expansion Phase Part 2 and Part 3**

	Expansion Cohort	TTI-621 Starting Dose (mg/kg/wk)	Combination Partner Dose
Monotherapy	IBCL (closed)	0.2	NA
	ABCL (closed)	0.2	NA
	TCL (closed)	0.2	NA
	CTCL	0.2	NA
	PTCL	0.2	NA
	HL (closed)	0.2	NA
	CLL (closed)	0.2	NA
	ALL (closed)	0.2	NA
	MM (closed)	0.2	NA
	AML (closed)	0.2	NA
	MDS (closed)	0.2	NA
	MPN (closed)	0.2	NA
Combination Therapy	Rituximab combination: CD20-positive malignancy	0.1	375 mg/m  /wk for up to 8 cycles a
	Nivolumab combination: cHL	0.1	per FDA approved package insert for cHL b

NA: not applicable

a Subjects may continue on TTI-621 monotherapy upon completion of combination partner regimen/unacceptable toxicity to the combination regimen

b Subjects who have unacceptable toxicity to the combination regimen may continue to receive TTI-621 monotherapy

### 3.3.2 Phase 1b Dose Optimization Part 4 (to be enrolled as of Amendment 9)

A minimum of 3 patients will be treated in each cohort sequentially in a 3 + 3 design. The planned dose escalation levels are shown in [Table 3-4](#). Patients will receive once weekly dosing of TTI-621 at the dose levels in their assigned cohort regimen (Week 1 given on Day 1, Week 2 given on Day 8, and Week 3 given on Day 15). The DLT observation period is 21 days. Patients will be considered evaluable for DLT if they receive all 3 weekly doses within the DLT evaluation period or if they experience an AE meeting DLT criteria during that time. If a patient experiences a non-DLT event that requires a dose to be held per dose modification guideline ([Section 6.5](#)), the DLT evaluation period can be extended to 28 days. If a DLT occurs in 1 of 3 patients within a cohort, 3 additional patients will be treated at that cohort regimen. In the absence of DLT, enrollment will proceed sequentially through the planned dose levels.

Alternative dose escalation including evaluation of intermediate doses, expansion of an existing dose level, evaluation of alternative regimens/schedules including a dose ramp-up design following different dose intensification increments and schedule, and modification of dosing frequency and/or IV infusion rate are all permissible if supported by the evolving data and a SRC decision. All patients in each cohort must have completed the 21-day DLT period before the next cohort begins treatment. The MTD of TTI-621 will be the dose below the one in which  $\geq 2$  DLTs are observed among 6 treated patients.

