In the starting dose cohort (0.5 mg/kg), the first 3 patients will be treated sequentially to allow close monitoring of toxicity and timely dose adjustment if needed. The third patient will not start the study treatment until the first and second patient, respectively, have completed the initial two weeks of study treatment and had no observation of treatment-emergent adverse events (TEAE) meeting DLT criteria. If the first or second patient experiences a DLT event within the first two weeks of treatment, de-escalation to Level 0, a priming dosing regimen, will be considered per SRC discussion and decision. A priming regimen refers to a dosing regimen that involves a lower priming dose used during the initial week(s) of treatment followed by further dose escalation to a higher and stable dose for continued use throughout the course of the study. At Level 0, patients will be dosed at 0.2 mg/kg for the first week and then receive a stable dose of 0.5 mg/kg for the remainder of the study.

If Level 0 is determined to be tolerable per 3+3 schema, further escalation of doses beyond 0.5 mg/kg in Week 2 and beyond will be considered, as part of the priming dosing regimen. The same dose escalation increment (to 0.7, 1.0, and 1.4 mg/kg) may be followed after the initial week of exposure to 0.2 mg/kg.

A DLT is defined in phase 1b dose optimization (Part 4) as any of the following TEAEs that occur during the 3-week DLT period (including pre-dose tests on Day 22) and that are considered at least possibly related to study treatment by the investigator. Note that any AEs for which the relationship to study treatment cannot be ruled out should be considered possibly related:

- Grade 4 thrombocytopenia (<25 × 10^9/L) lasting >72 hours or a platelet count ≤10 × 10^9/L at any time
- ≥ Grade 3 thrombocytopenia with bleeding (except epistaxis or gingival bleeding that is less than 24 hours in duration and does not require medical intervention, or normal menses) or requiring platelet transfusions

- Grade 4 anemia, unexplained by underlying disease
- Grade 4 neutropenia lasting >72 hours
- Grade 3 febrile neutropenia lasting >72 hours
- Grade 4 febrile neutropenia
- Grade 3 or higher non-hematologic toxicity with the following exceptions:
  - Grade 3 nausea and/or vomiting lasting <72 hours with standard supportive care
  - Transient Grade 3 fatigue lasting ≤72 hours

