  - Transient asymptomatic Grade 3 laboratory abnormalities considered not clinically significant following agreement between investigators and the sponsor's medical monitor and that last <72 hours with standard supportive care
- Other ≥ Grade 2 TTI-621-related non-hematologic toxicities that, in the opinion of the investigator, require a dose reduction or discontinuation of TTI-621

The major revision of the DLT criteria in comparison to those in phase 1a is that Grade 4 thrombocytopenia is no longer a DLT unless it lasts for more than 72 hours. This revision is based on a safety analysis of 179 patients by a data cut of 01 October, 2018. The majority of patients (143; 80%) had abnormal platelet counts reported at 1 or more timepoints post-dose, with 49 subjects (27%) experiencing Grade 4 decreases, including both TTI-621-induced events, and events resulting from the underlying hematologic malignancies. As shown in Figure 1-3 (See Section 1.8.4), reduced platelet counts that occurred on dosing days generally recovered within the week prior to the next dose. Overall, pre-infusion platelet counts remained stable over the course of the study. Due to the transient and reversible nature of the thrombocytopenia, no apparent increase in the incidence of bleeding has been observed on study (Table 1-1, Section 1.8.4). A total of 24/179 subjects (13%) experienced a treatment-emergent bleeding event in Study TTI-621-01 (see Table 1-1, Section 1.8.4). Overall, 20/179 subjects (11%) experienced Grade 1 or 2 events and 4 subjects (2%) had Grade 3 events. Grade 3 hemorrhage events were considered treatment-related for 3 subjects (2%). No Grade 4 hemorrhage events were reported. Therefore, relaxing the original DLT criteria is appropriate after the clinical significance of thrombocytopenia is better assessed with an expanded safety data set.

The MTD is defined as the dose level immediately below the lowest dose that at which 2 or more of either 3 or 6 patients experienced a DLT during the 3-week DLT period. At least 6 patients must be treated at the putative MTD, with no more than 1 incidence of DLT. AEs that occur after the 3-week DLT period or cumulative toxicities will be considered in the final designation of MTD.

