**Table 3-4: Planned Dose Escalation Levels**

Level	N	TTI-621 dose (mg/kg)		
		Week 1b	Week 2	Week 3
0	3 (+ 3)	0.2	0.5	0.5
1 a	3 (+ 3)	0.5	0.5	0.5
2	3 (+ 3)	0.7	0.7	0.7
3	3 (+ 3)	1.0	1.0	1.0
4	3 (+ 3)	1.4	1.4	1.4

a Level 1 = starting dose

b If de-escalation to level 0 is required, all subsequent cohorts will start with a priming dose of 0.2 mg/kg at week 1 followed by the respective dose level escalation increments (0.7, 1.0, 1.4 mg/kg) at week 2 or subsequent weeks, as applicable, based on SRC decision.

In the starting dose level (0.5 mg/kg), the first 3 patients will be treated sequentially to allow close monitoring of toxicity and timely dose adjustment if needed. The third patient will not start the study treatment until the first and second patient, respectively, have completed the initial two weeks of study treatment and had no observation of TEAEs meeting DLT criteria. If the first or second patient experiences a DLT event within the first two weeks of treatment, de-escalation to Level 0, a priming dosing regimen, will be considered per SRC discussion and decision. A priming regimen refers to a dosing regimen that involves a lower priming dose used during the initial week(s) of treatment followed by further dose escalation to a higher and stable dose for continued use throughout the course of the study. At Level 0, patients will be dosed at 0.2 mg/kg for the first week and then receive a stable dose of 0.5 mg/kg for the remainder of the study.

If Level 0 is determined to be tolerable per 3+3 schema, further escalation of doses beyond 0.5 mg/kg in Week 2 and beyond will be considered, as part of the priming dosing regimen. The same dose escalation increment (to 0.7, 1, and 1.4 mg/kg) may be followed after the initial week of exposure to 0.2 mg/kg.

The MTD is defined as the dose level immediately below the lowest dose that at which 2 or more of either 3 or 6 patients experienced a DLT during the 3-week DLT period. At least 6 patients must be treated at the putative MTD, with no more than 1 incidence of DLT. AEs that occur after the 3-week DLT period or cumulative toxicities will be considered in the final designation of MTD.

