### **3.3.3 Definition of Dose-limiting Criteria for Phase 1b Part 4 (Amendment 9)**

Dose-limiting toxicity is defined as any of the following TAEs that occur during the 21-day DLT treatment/observation period (including the pre-dose tests on Day 22/Week 4 Day 1) and that are considered at least possibly related to study treatment by the investigator. Note that any AEs for which the relationship to study treatment cannot be ruled out should be considered possibly related:

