#### 6.6 Intra-patient Dose Reduction and Escalation (Phase 1b Dose Optimization Part 4: DLT evaluation period)

Intra-patient dose reductions of TTI-621 are not permitted in the DLT evaluation period (Week 1-3) in the phase 1b dose optimization unless the patient experiences a DLT attributed to TTI-621. If a patient experiences a DLT during the first 21 days, treatment should be held and the event counted toward the assessment of MTD for the given cohort. These patients may continue in the study upon resolution of the toxicity at a reduced dose

level. Patients who receive a reduced dose of TTI-621 during the DLT evaluation period for reasons other than DLT will be replaced.

During phase 1b dose optimization, when the MTD or recommended phase 2 dose of TTI-621 is determined, all patients who have received TTI-621 at a dose lower than the recommended dose for a minimum of 4 weeks may dose escalate to the recommended dose in the absence of PD or unacceptable treatment-related toxicity at the investigator's discretion and with the medical monitor's approval. Patients for whom an increase in the dose of TTI-621 is being considered must have TEAEs resolve to  $\leq$ Grade 1 or baseline or to a level that is acceptable to the investigator (non-hematologic toxicity must be  $\leq$ Grade 2, hematologic toxicities must be recovered to levels above the minimum requirement for TTI-621 dosing).

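### Part 4 lets the DLT period run to 28 days after a held dose, but the DLT definition, MTD rule, Section 6.6 and cohort gate still stop at 21 days; the SAP also drops held patients whom the protocol treats as evaluable

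*Protocol*

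**What the plan says.** Protocol Section 3.3.2 gives Part 4 patients weekly doses on Days 1, 8 and 15 and sets a 21-day DLT observation period. A patient is evaluable after receiving all three doses within the DLT evaluation period, or after a DLT in that time. If a non-DLT event requires a held dose, "the DLT evaluation period can be extended to 28 days".

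The rules that depend on the period state a fixed length and do not mention the extension:

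- Cohort gate (Section 3.3.2): "All patients in each cohort must have completed the 21-day DLT period before the next cohort begins treatment".
- DLT definition (synopsis): "any of the following TEAEs that occur during the 3-week DLT period (including pre-dose tests on Day 22".
- DLT definition (Section 3.3.3): "that occur during the 21-day DLT treatment/observation period (including the pre-dose tests on Day 22/Week 4 Day 1".
- MTD rule (synopsis, repeated in Section 3.3.2): "2 or more of either 3 or 6 patients experienced a DLT during the 3-week DLT period".
- Section 6.6: "Intra-patient dose reductions of TTI-621 are not permitted in the DLT evaluation period (Week 1-3) in the phase 1b dose optimization", and "If a patient experiences a DLT during the first 21 days, treatment should be held and the event counted toward the assessment of MTD".

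Section 6.5.2 delays a dose by one week when retreatment criteria are not met. Section 7 allows 2 days either side of a scheduled treatment day.

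SAP Section 2 defines one DLT-evaluable set for Part 1 and non-Q2W Part 4. It sets the period at the first 21 days, makes a patient unevaluable after a non-DLT delay of more than 3 days, and then extends observation to 7 days beyond the third dose for patients with a delay. In the protocol the 3-day limit appears only for Phase 1a (Section 3.2.1).

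**The concern.** The per-cohort DLT count drives each escalation and the MTD. For a patient with a held dose, the protocol does not settle two things: whether a DLT after the third dose counts, and whether the week after that dose must be observed before a higher level opens. Investigators, the Safety Review Committee (SRC) and programmers could treat the same event differently.

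Holds are foreseeable. Section 6.5.2 sets platelet and neutrophil thresholds before each dose, Part 4 no longer counts Grade 4 thrombocytopenia as a DLT solely because it occurs, and the 28-day clause itself anticipates held doses.

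The SAP raises a separate reporting problem: its number of DLT-evaluable patients can differ from the number on which the protocol's rules operated.

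**Working it through.** **Inputs.** Doses on Days 1, 8 and 15, with a period of 21 days extendable to 28 (protocol 3.3.2). Hold of 7 days (6.5.2). Visit window of ±2 days (Section 7). SAP delay limit of 3 days and extension of 7 days beyond the third dose (SAP Section 2).

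**Formula.** Counted days from dose 3, infusion day included = period end − dose-3 day + 1, with a floor of 0.

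**Step 1: the plan's own period.** With no hold, dose 3 is on Day 15 and its dosing week ends on 15 + 6 = Day 21. That reproduces the 21-day period and gives 21 − 15 + 1 = 7 counted days.

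**Step 2: a one-week hold.** Holding dose 2 gives Days 1, 15, 22; holding dose 3 gives Days 1, 8, 22. Either way dose 3 is on Day 22 (Days 20 to 24 with the window).

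| Case | Dose-3 day | Period end | Counted days |
|---|---|---|---|
| No hold | 13 / 15 / 17 | 21 | 9 / 7 / 5 |
| Held, numeric rules | 20 / 22 / 24 | 21 | 2 / 0 / 0 |
| Held, extension applied | 20 / 22 / 24 | 28 | 9 / 7 / 5 |

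Only two of the three doses required for evaluability fall by Day 21, unless dose 3 is given early, on Day 20 or 21. The Day 22 pre-dose tests named in the DLT definition do not help: for a patient dosed on Day 22 they come just before the third infusion.

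**Step 3: the SAP set.** The delay is 7 days, and at the shortest 20 − 15 = 5 days. Both exceed 3, so a held patient without a DLT is excluded. The SAP's extension would carry observation to 22 + 7 = Day 29 (Day 28 if the infusion day is counted as the first of seven), but the exclusion still removes the patient. The longest delay that stays evaluable is 3 days: dose 3 on Day 18, observation to Day 25.

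**Step 4: where the SAP set is used.** SAP 3.1 reports its size under disposition. DLT tables fall under SAP 3.5 and 3.5.1, which use the Safety Analysis Set. Escalation is decided by the SRC (protocol 3.4), and the SAP covers the abbreviated study report. As an example, take a level with six patients, one held for a week without a DLT. The protocol can count six as evaluable; the SAP counts 6 − 1 = 5, below the six that protocol 8.3 requires at the selected dose.

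**The case against.** The best defence is that the extension is a specific exception written next to the general rule, and that extending a patient's period makes little sense if events in the added week do not count. Section 3.3.2 ties evaluability to the evaluation period without repeating a number, and SAP 1.1.3 refers to the DLT period without a length. This is a reasonable reading, and the sponsor may well intend it. But the DLT definition names Day 22, Section 6.6 equates the same term with Weeks 1 to 3, and the gate states 21 days.

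The SRC also stands between cohorts. It meets when all 3 or 6 subjects are evaluable (protocol 3.4), so review would probably wait for a held patient's third dose. It need not wait for the week after. Likewise, "AEs that occur after the 3-week DLT period or cumulative toxicities will be considered in the final designation of MTD" brings later events into a final judgement, not into the per-cohort count or the gate.

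A reader might infer three stronger points, which the documents do not support:

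- *That held patients have already shown drug toxicity and most need watching after dose 3.* Sections 6.5.1 and 6.5.3 (Table 6-1) also allow doses to be withheld for events unrelated to the drug. Section 1.7 describes platelet falls within 24 hours that attenuate with weekly exposure, and infusion reactions typically after the first infusion only.
- *That the rise in escalation probability is known.* The 3+3 formula (1−p)³ + 3p(1−p)²(1−p)³ gives 0.49 at p = 0.30, matching the SAP 1.2.2 table. If DLT hazard were equal across dosing weeks and the last week uncounted in held patients, their p would be 1 − 0.70^(2/3) = 0.212. The probability would then be 0.55, 0.62 or 0.68 with 1, 2 or 3 of every 3 patients held. Equal hazard sits poorly with Section 1.7, and the documents give no hold rate, so I place no weight on these figures.
- *That the SAP rule alters escalation or the DLT summaries.* Step 4 shows that it does not. Why the SAP carries the rule is also unknown, since its version history cites notes-to-file that are not available here.

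**Conclusion.** The point stands as an inconsistency between stated rules, and it should be fixed. Followed as written, the numeric rules leave a patient held for one week with 0 counted days from dose 3 (0 to 2 across the visit window) instead of 7, and allow the next dose level to open without that week. This assumes a hold of exactly one week and a literal reading. The documents do not establish that any DLT would in practice go uncounted. SRC review and late-event consideration reduce the risk by judgement only. The frequency of holds and the effect on escalation cannot be derived.

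The SAP discrepancy is real but narrower. It changes the reported DLT-evaluable set by removing one-week-held patients without a DLT, and leaves SRC decisions and DLT summaries untouched.

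**What to change.** Define the Part 4 DLT period once: 21 days including the Day 22 pre-dose tests or, if a dose is held for a non-DLT event, through 7 days after the third dose (about Day 28 to 29 for a Day 22 dose). Anchoring to the third dose agrees with the extension sentence already in the SAP. It is better than a fixed Day 28 end, which leaves only 5 counted days after a Day 24 dose.

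Use the defined term in the DLT definition (synopsis and Section 3.3.3), both statements of the MTD rule that give a length, Section 6.6 and the cohort gate. Require every patient in a cohort to complete the period before the next cohort starts.

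In SAP Section 2, keep the extension to 7 days beyond the third dose and limit the 3-day-delay exclusion to Part 1.

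The cost is wording in two documents and, when a dose was held, a next cohort that opens up to about one week later. No patients or visits are added.
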